13.6. Vital Signs

Summary statistics for actual values and change from baseline will be tabulated for vital signs by disease group, cohort and treatment at each scheduled visit.

13.7. Physical Examination

Physical examination will be listed.

13.8. Electrocardiogram

The ECG parameters (heart rate, PR interval, QRS interval, QT interval, and QTcF interval) at each time recorded as well as the change from baseline will be summarized with descriptive statistics by disease group, cohort and treatment. These parameters will be determined electronically by the ECG machine at the clinical site. QTcF will be calculated using Fridericia's formula.

The overall ECG assessment will be reported as "Normal," or "Abnormal – not clinically significant," or "Abnormal – clinically significant" with respect to relevant abnormalities by the Investigator. A shift table comparing the ECG assessment over the treatment period to baseline will be presented by disease group, cohort and treatment.

14. PHARMACOKINETIC ANALYSES

PK parameters for OMS721 will be calculated using non-compartmental analysis. Only concentrations greater than or equal to the validated lower limit of quantitation (LLOQ) will be used in the PK analyses. Actual blood sampling times will be used in all PK analyses. Per protocol times will be used to calculate mean concentrations for graphical displays. The maximum concentration (C_{max}) and time to maximum concentration (T_{max}) will be taken directly from the individual's data. The elimination rate constant, λ_z , will be calculated as the negative of the slope of the terminal log-linear segment of the time-concentration curve. The range of data to be used for each subject and treatment will be determined by visual inspection of a semi-logarithmic plot of concentration versus time and will be comprised of at least three data points along the elimination phase. Elimination half-life ($t_{1/2}$) will be calculated according to the following equation:

$$t_{1/2} = \frac{0.693}{\lambda_z}$$

The area under the curve (AUC) of the final sample with a concentration \geq LLOQ [AUC(0-t)] will be calculated using the linear trapezoidal method and extrapolated to infinity [AUC(inf)] using:

$$AUC(inf) = AUC(0-t) + \frac{C_{tf}}{\lambda_z}$$

where C_{tf} is the final concentration \geq LLOQ.

Clearance (CL) will be calculated by $Dose/AUC$. Volume of distribution will be calculated by $Dose/\lambda_z \times AUC$.

Concentrations and derived PK parameters will be summarized using descriptive statistics. Graphs of individual subject and mean concentrations, by disease group and cohort, will be presented on linear and semi-logarithmic axes.

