10.1.13. Cohort 3 Re-Treatment Visits RT2 – RT12 (+/- 2 days)

Study drug will be administered once per week for a total of 12 weekly doses during the study. The following procedures will be performed:

Prior to administering the dose of study drug, the following procedures will be performed:

1. Vital signs including BP, pulse rate, RR and temperature (after at least 5 minutes of rest).
2. AEs and concomitant medications will be recorded.
3. ECG taken (after at least 5 minutes of rest in the supine position) (re-treatment visit 12 only).
4. Laboratory samples will be collected for:
 - Hematology, chemistry, coagulation, cystatin C (re-treatment visit 2, re-treatment visit 5, and re-treatment visit 9)
 - Urinalysis (re-treatment visit 2 and re-treatment visit 9)
 - Urine for inflammatory biomarkers (re-treatment visit 2 and re-treatment visit 9)
 - Blood samples for future research (re-treatment visit 2, re-treatment visit 5, and re-treatment visit 9)
 - Serum PK sample (re-treatment visit 2, re-treatment visit 5, re-treatment visit 9, and re-treatment visit 12)
 - Serum PD sample (re-treatment visit 2, re-treatment visit 5, re-treatment visit 9, and re-treatment visit 12)
 - Serum ADA sample (re-treatment visit 5 and re-treatment visit 9)

CONFIDENTIAL

No use, disclosure or reproduction outside of Omeros without prior written authorization

- Serum or urine pregnancy test in women of childbearing potential. If the test result is positive then the subject will be excluded from further treatment, but continue follow-up (re-treatment visit 5 and re-treatment visit 9)

Study drug will be administered by IV infusion over 30 minutes.

After dosing with study drug, the following procedures will be performed:

1. Vital signs will be taken including BP, pulse rate, RR, and temperature (after at least 5 minutes of rest) at the following timepoint: 30 minutes.
2. ECG taken (after at least 5 minutes of rest in the supine position), to be obtained immediately post dose (re-treatment visit 12 only).
3. Serum PK samples will be taken at the following timepoints at the end of dosing: 5 minutes and 2 hours (re-treatment visit 12 only)
4. Serum PD samples will be taken at the following timepoints at the end of dosing: 2 hours (re-treatment visit 12 only)

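### SAP Section 14 misprints the volume formula, names neither the AUC nor the dose behind clearance, and excludes values below LLOQ with no exception for concentration summaries

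*SAP*

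**What the plan says.** SAP Section 14 sets out a non-compartmental analysis.

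- **Volume:** "Volume of distribution will be calculated by $Dose/\lambda_z \times AUC".
- **Clearance:** "Clearance (CL) will be calculated by $Dose/AUC". It does not say which AUC, or after which dose.
- **AUC:** only two are defined. AUC(0-t) runs to the last quantifiable sample; it "will be calculated using the linear trapezoidal method and extrapolated to infinity" to give AUC(inf). There is no AUC over a dosing interval.
- **λz:** the data range "will be comprised of at least three data points along the elimination phase".
- **LLOQ:** "Only concentrations greater than or equal to the validated lower limit of quantitation (LLOQ) will be used in the PK analyses".
- **Summaries:** "Concentrations and derived PK parameters will be summarized using descriptive statistics", with graphs of individual and mean concentrations. No separate rule is given for values below LLOQ.

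SAP Section 6 lists PK concentrations and parameters among the secondary endpoints. The Protocol synopsis plans serum concentration summaries by visit, disease and cohort. Protocol 13.2.6 assigns PK parameters to a separate pharmacokinetic analysis plan; SAP Section 14 neither cites that plan nor defers to it.

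**The concern.** There are three gaps in one section.

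First, the volume expression as printed does not have the units of a volume.

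Second, study drug is given weekly for 12 doses and PK is sampled around both the first and the last dose. Dose/AUC means different things depending on which AUC and which dose are used, and the text lets the analyst choose.

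Third, the LLOQ sentence applies to the PK analyses as a whole. If it is followed in the concentration summaries, subjects whose drug has become unmeasurable leave the average, and the mean describes only those who still have drug. No count below LLOQ is required, so a reader could not see this happening.

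At stake is whether a secondary endpoint can be reproduced and read correctly, including in Cohort 3, where the fixed 370 mg dose replaces weight-based dosing. No hypothesis test or decision rule depends on it.

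**Working it through.** **Inputs from the documents.** Weekly dosing, so an interval of 168 h (Protocol 10.1.4). Dose-1 samples: pre-dose, 5 min, 2 h, 24 h and 72 h, then pre-dose on Day 8 (Protocol 10.1.3, 10.1.4). Dose-12 samples: pre-dose and 30 min, then Day 85 and Day 120 (Protocol 10.1.8 to 10.1.10). Re-treatment dose 12: pre-dose, 5 min and 2 h, then one week later (Protocol 10.1.13, 10.1.14).

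**Assumed, because the documents do not give them.** One compartment; half-life 48 to 168 h; volume 5 L for the illustration; lognormal concentrations with CV 50% or 100%; a range of shares below LLOQ.

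**Volume.** The correct form is V = Dose/(λz × AUC), so Dose/λz = V × AUC. Multiplying by AUC, as printed, gives V × AUC², in mg²·h²/L. Take 370 mg, V = 5 L and a half-life of 120 h. Then λz = 0.693/120 = 0.00578 per h and AUC = 370/(0.00578 × 5) ≈ 12,810 mg·h/L. The printed expression gives about 8.2 × 10⁸ in hours, or 1.4 × 10⁶ if time is in days. The bracketed form returns 5 L in either unit.

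**Clearance.** Let r = 2^(−168/half-life) and treat the short infusion as instantaneous.

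- Dose/AUC(inf) after dose 1 equals true CL.
- Dose/AUC(0-t) to Day 8 after dose 1, relative to true CL, is 1/(1 − r).
- Dose/AUC(inf) after dose 12, relative to true CL, is (1 − r)/(1 − r¹²), because the area includes carry-over from the 11 earlier doses.

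| Half-life | r | AUC(0-t), dose 1 | AUC(inf), dose 12 |
|---|---|---|---|
| 48 h | 0.088 | 1.10 | 0.91 |
| 72 h | 0.198 | 1.25 | 0.80 |
| 96 h | 0.297 | 1.42 | 0.70 |
| 168 h | 0.500 | 2.00 | 0.50 |

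At 168 h, two analysts who both follow the text could differ by 2.00/0.50 = 4 times.

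The linear trapezoid at the dose-1 sampling times matters less. Dose/AUC(inf) then gives 0.95 of true CL at a 2-day half-life and 0.97 to 1.00 at 3 days or more; it falls to 0.88 only at 1 day.

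**LLOQ.** Follow-Up Visit 2 is Day 120 and the last dose is Day 78, a gap of 42 days or 1,008 h. The concentration relative to peak is 2^(−1008/72) = 2^(−14) ≈ 0.006% at a 72 h half-life and 2^(−1008/168) = 2^(−6) ≈ 1.6% at 168 h. Values below LLOQ are therefore plausible there, although the LLOQ itself is not stated.

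For a lognormal with σ² = ln(1 + CV²) and a share p below LLOQ, the mean of the retained values divided by the true mean is Φ(σ − z_p)/(1 − p), where z_p is the normal quantile at p.

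| Share below LLOQ | CV 50% | CV 100% |
|---|---|---|
| 0% | 1.00 | 1.00 |
| 10% | 1.07 | 1.09 |
| 25% | 1.17 | 1.25 |
| 50% | 1.36 | 1.60 |

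**The case against.** The strongest reply is that these are drafting points.

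- **Volume.** A lost bracket is the obvious explanation, and standard PK software would compute volume correctly. That is likely. If the signed SAP sets the formula as a fraction with λz × AUC below the bar, this item falls away; otherwise the text needs correcting.
- **Clearance.** The SAP never orders clearance after dose 12. The full profiles are at dose 1 and the first re-treatment dose, and the three-point requirement for λz may rule out dose 12: Treatment Visit 12 reaches three post-dose points only if Day 120 is quantifiable, and the re-treatment dose-12 profile relies on samples at 5 min and 2 h. This stands against any claim that clearance will be wrong. It does not remove the ambiguity, because AUC(0-t) after dose 1 also fits the text.
- **LLOQ.** Section 14 gives mean graphs their own rule on sampling times, so the LLOQ sentence could be meant for parameter estimation only. That reading is possible, but it is not what the sentence says in a section on pharmacokinetic analyses that also plans the summaries.
- **Other documents.** The PK analysis plan or the separate table shells (SAP 20.1) may settle these points. Neither is available, and Section 14 states its own rules. If that plan differs, the conflict still has to be resolved.

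A reader might go further and infer that volume, clearance and weekly troughs will all come out wrong, with clearance too low. The documents do not support that. Dose-1 clearance from AUC(inf) is valid, and the direction of any error depends on the AUC chosen. The LLOQ exclusion hardly touches clearance or volume, since AUC runs to the last quantifiable value and is then extrapolated. Nothing shows how many troughs fall below LLOQ, and Protocol 7.2.1 describes pathway inhibition for about one week. Nor can a large trapezoid error over the dose-12 interval be charged to the plan, because the SAP defines no such AUC.

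**Conclusion.** The point holds as a defect of specification. The volume formula is wrong as printed; this needs no assumption beyond the printed text being faithful. The clearance rule is incomplete: one permitted reading is sound, and two others give 1.10 to 2.0 times or 0.91 to 0.50 of true clearance, under a one-compartment model with half-lives of 48 to 168 h. The LLOQ rule, taken at its word, biases visit means upward wherever values fall below LLOQ. The size depends on a share the documents do not give: zero if none, about 17% to 25% at a quarter, and 36% to 60% at half. The analyses are descriptive and the study is unpowered, so this should be corrected before the PK tables are produced, but it does not threaten the study's conclusions on safety or proteinuria.

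**What to change.** Amend SAP Section 14 as follows.

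- Write V = Dose/(λz × AUC(inf)).
- State CL = Dose/AUC(inf) for dose 1, and for a first re-treatment dose with no measurable pre-dose drug. For any repeat dose at which CL is reported, define AUC over the dosing interval and use Dose divided by that AUC.
- Limit the LLOQ exclusion to the λz fit and the endpoint of the AUC.
- In concentration summaries, report at each visit the number below LLOQ and the median over all sampled OMS721 subjects, ranking values below LLOQ lowest. Apply the same rule to the graphs of average concentration.
- Optionally, use linear-up/log-down trapezoids. The gain at dose 1 is small: about 6% of AUC at a 48 h half-life and 1% at 96 h.
- State whether SAP Section 14 or the PK analysis plan named in Protocol 13.2.6 governs.

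The cost is SAP wording and slightly more tabulation. No new samples or visits are needed.

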15. PHARMACODYNAMIC ANALYSES

The extent of *ex vivo* lectin pathway activation will be calculated relative to the subject's baseline (pre-dose) result. The lectin pathway activity of post-dose samples is expressed as % inhibition relative to baseline. The lectin pathway activity will be summarized by disease, cohort and treatment at each scheduled time point.

16. PHARMCOKINETIC-PHARMACODYNAMIC ANALYSES

OMS721 concentration and lectin pathway activity will be plotted to explore their relationship.

17. IMMUNOGENICITY ANALYSES

The presence of ADA will be summarized by disease, cohort and time. The presence of Nab will be summarized by disease, cohort and time.

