5. OMS721 PK
6. OMS721 PD
7. Urine protein/creatinine ratio change from baseline to 12 weeks by disease
8. Change from baseline in serum creatinine by disease
9. Change from baseline in eGFR calculated using the following equations by disease state: MDRD equation, CKD-EPI using serum creatinine, CKD-EPI using cystatin C, and CKD-EPI using creatinine – cystatin C
10. Occurrence of ADA and NAb
11. Urine inflammatory markers by disease
12. Duration of therapeutic response, if observed, defined as 24-hour urine protein < 50% of baseline for up to 104 weeks (Cohort 2 only)

Statistical Methods:

Sample Size Determination

The primary objective of the study is to assess safety and tolerability of OMS721. The sample size has been empirically determined for each cohort.

Analysis Populations

Safety analyses will be based on the safety population, which includes all subjects who receive any amount of study drug.

Efficacy analyses will be based on the efficacy population, which includes all subjects who receive any amount of study drug and have a baseline and at least one post-baseline 24-hour urine protein.

Statistical analyses will group subjects according to their assigned cohort, except for the rollover subjects who will constitute their own cohort.

Safety Analyses

The safety endpoints will be descriptively summarized. Adverse events will be coded according to preferred term and system/organ class using the Medical Dictionary for Regulatory Activities (MedDRA) AE coding dictionary. Laboratory tests and vital signs will be summarized by visit.

CONFIDENTIAL

No use, disclosure or reproduction outside of Omeros without prior written authorization

Efficacy Analyses

The efficacy endpoints will be descriptively summarized by visit, disease and cohort.

Pharmacokinetic Analyses

Serum drug concentration will be summarized by visit, disease, and cohort. Non-compartmental models will be used to estimate the PK parameters. ADA information will be summarized by visit.

CONFIDENTIAL

No use, disclosure or reproduction outside of Omeros without prior written authorization

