13.2.9. Immunogenicity Analyses

The presence of ADA and the presence of NAb will be summarized by disease, cohort, and time.

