PD Sampling pre-dose			X			X	X	X	X	X	X	X	X			
PD Sampling post dose: 30 min						X		X			X		X			
PD Sampling post dose: 2 hours			X													
ADA Sampling														X	X	X
ADA Sampling pre dose			X					X			X					
Adverse Events		X	X	X	X	X	X	X	X	X	X	X	X	X	X	X
Concomitant medications/therapies	X	X	X	X	X	X	X	X	X	X	X	X	X	X	X	X

SCR = screening; ECG = electrocardiogram; HIV = human immunodeficiency virus; PD = pharmacodynamics; PK = pharmacokinetics; ADA = anti-drug antibody; NAb = Neutralizing antibody

1. Instruct the subject on how to collect and provide supplies. At Follow-Up Visit 2, urine collection supplies are dispensed if the subject is not going into the Retreatment Period. No supplies are dispensed at the last Follow-Up Visit (FU9).
2. Collect first void urine on each of three mornings, 1st void urine samples.
3. Urinalysis tests include color, specific gravity, pH, glucose, protein, bilirubin, urobilinogen, blood, ketone, nitrite, leukocyte esterase and microscopic if required (red blood cells, white blood cells and bacteria).
4. The following laboratory assessments will be performed in this study:
 - Chemistry tests include glucose, urea nitrogen, creatinine, total protein, albumin, total bilirubin, alkaline phosphatase, ALT, AST, calcium, sodium, potassium, chloride, and bicarbonate
 - Hematology tests include white blood cell count with automated differential (neutrophils, segmented neutrophils, lymphocytes, monocytes, eosinophils and basophils), red blood cell count, hemoglobin, hematocrit, mean corpuscular volume, mean corpuscular hemoglobin, mean corpuscular hemoglobin concentration, red cell distribution width, and platelet count
 - Coagulation tests include PT, PTT and INR
5. Anti-PLA2R is only to be performed for subjects with membranous nephropathy.
6. Pregnancy test must be via serum for Screening Visit 1. May be urine or serum for all other visits.
7. ECG collected post-dose before 5-minute PK sample.

Note: Procedures with a specified time frame will be considered per protocol if they are performed within the following windows: vital signs on dosing days ± 5 minutes in the first hour of start of dosing and ± 10 minutes thereafter; PK and PD draws on the day of dosing ± 5 minute; PK draws Days 2 and 4 ± 2 hours. If multiple procedures are specified at one timepoint they should be performed in the following order: blood draw and then vital signs, with the blood draw at the exact specified time.

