6. STUDY ENDPOINTS

The primary endpoints are:

- Safety and tolerability of OMS721 as assessed by AEs, vital signs, clinical laboratory tests, and ECGs

The secondary endpoints are:

- 24-hour urine protein change from baseline to 12 weeks
- Urine albumin/creatinine ratio change from baseline to 12 weeks
- Corticosteroid dose needed to maintain stable renal function (Cohort 1)
- PK concentration and PK parameters of OMS721
- PD measure of inhibition of *ex vivo* lectin pathway activation

The exploratory endpoints are:

- Urine protein/creatinine ratio by disease
- Serum creatinine by disease
- eGFR by disease calculated by the MDRD equation, the CKD-EPI equation using serum creatinine, the CKD-EPI equation using cystatin C, and the CKD-EPI equation using creatinine – cystatin C
- Occurrence of ADA and Nab
- Urine inflammatory markers by disease
- Duration of therapeutic response, if observed, defined as the number of the longest consecutive weeks that 24-hour urine protein < 50% of the baseline for up to 104 weeks (Cohort 3 only)

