8.2. Study Visits

8.2.1. Baseline

The analysis value for urine albumin/creatinine ratio is defined as the average of all the values obtained at a timepoint. The planned number of urine albumin/creatinine ratios is three at each scheduled timepoint. The baseline value of the urine albumin/creatinine ratio is defined as the average of the analysis values from the two screening visits. The analysis value for urine protein/creatinine ratio is defined in the same fashion.

For all other study variables, the baseline value is defined as the last non-missing value prior to the first study drug administration.

8.2.2. Day 1

Study Day 1 is defined as the first dose date of study treatment.

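### SAP 17 plans ADA and NAb presence by time only: later results are not linked within subject to the pre-dose sample, and there is no subject-level incidence and no split by treatment

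*SAP*

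**What the plan says.** SAP 17 consists of two sentences: "The presence of ADA will be summarized by disease, cohort and time" and "The presence of Nab will be summarized by disease, cohort and time". Protocol 13.2.9 plans the same thing: "The presence of ADA and the presence of NAb will be summarized by disease, cohort, and time". The protocol synopsis, under pharmacokinetic analyses, adds only "ADA information will be summarized by visit".

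These summaries serve the exploratory endpoint listed in SAP 6 as "Occurrence of ADA and Nab". SAP 3.3 places it among objectives that describe the effect of OMS721.

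A sample before first dose exists. The schedules in SAP 5.1 and Protocol 19.2 carry a row for "ADA Sampling pre dose" marked at T1, T5 and T9, and a further ADA row marked at FU1, FU2 and the Cohort 3 extended visits. SAP 8.2.1 supplies a general baseline rule: "For all other study variables, the baseline value is defined as the last non-missing value prior to the first study drug administration".

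Neither document defines pre-existing or treatment-emergent ADA or NAb, compares a subject's later results with the pre-dose result, or plans a count of subjects ever positive.

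**The concern.** Occurrence of antibody, read as an effect of the drug, is a statement about subjects: how many who were negative before dosing became positive afterwards. A count of positives at each visit is a statement about visits. It does not say whether the positives at two visits are the same people, or whether a positive after dosing was already positive before it.

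The same SAP makes the link elsewhere. For pharmacodynamics, SAP 15 says: "The lectin pathway activity of post-dose samples is expressed as % inhibition relative to baseline". For adverse events, SAP 13.1 defines treatment emergence and reports subject incidence. Immunogenicity has neither.

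SAP 17 also leaves out treatment as a grouping factor, whereas SAP 15 and the efficacy sections name it. Cohorts 2 and 3 each contain a vehicle arm, so a table by disease and cohort alone may mix subjects who have received OMS721 with subjects who have not.

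What is at stake is whether the planned output can answer the immunogenicity objective. No primary or secondary endpoint depends on it.

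**Working it through.** The documents state no ADA or NAb rate, so there is no planned figure to reproduce. The check asks how far a by-time table determines subject-level incidence.

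**Inputs**
- Sampling times to Week 18 (SAP 5.1, Protocol 19.2): T1 pre-dose, T5, T9, FU1, FU2. That is one sample before first dose and four after it.
- Group size for illustration: about 18 subjects in Cohort 3 (SAP 4), randomised 1:1 (Protocol 9.1.2), so 18/2 = 9 per arm.
- Assumptions: all five samples are available for all n = 9 subjects, and exactly k subjects are positive at each time.

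**Formulas**
- Ever positive after dosing: at least k (the same subjects every time), at most min(n, 4k).
- Newly positive among the n − k subjects negative at T1: at least 0, at most min(n − k, 4k).

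**Results, with the by-time table held fixed**

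| k per time | Ever positive post-dose | Newly positive |
|---|---|---|
| 1 | 1 to min(9, 4) = 4 of 9 (11.1% to 44.4%) | 0 to min(8, 4) = 4 of 8 (0% to 50%) |
| 2 | 2 to min(9, 8) = 8 of 9 (22.2% to 88.9%) | 0 to min(7, 8) = 7 of 7 (0% to 100%) |

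Listing every assignment for k = 1 gives the same limits.

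**The other end of the range.** The upper limits need positivity to be transient. Suppose instead that four subjects turn positive by T5 and stay positive. T5, T9, FU1 and FU2 then each show those four, 4/9 = 44.4%, which is the full incidence. Where positivity always persists, the rise from T1 to the last visit also gives the number newly positive. The gap depends on how long positivity lasts, which the documents do not state.

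**Pooling of arms.** The figures with denominator 9 describe a single arm. If Cohort 3 is shown without a treatment split, one positive subject is 1/18 = 5.6 points, against 1/9 = 11.1 points by arm. For example, 2 of 9 on OMS721 (22.2%) and 0 of 9 on vehicle would appear as 2/18 = 11.1%.

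**Longer follow-up.** Cohort 3 adds ADA samples at seven extended visits (FU3 to FU9) and, for each re-treatment course, at RT1, RT5, RT9 and the re-treatment follow-up visit. More visits give more room for different subjects to be positive at different times. Subjects first given vehicle may also start open-label OMS721 in this period.

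**The case against.** The case for leaving the plan alone has several parts.

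- **The pre-dose sample is in the table.** T1 is one of the sampling times, so positivity before treatment is visible at group level. This stands; only the within-subject link is missing.
- **Incidence can be derived.** The samples are scheduled and SAP 8.2.1 already yields a baseline status. This also stands. A reader might infer that incidence is lost altogether, but the limit is on the planned summary and not on the data.
- **SAP 17 does not attribute positives to the drug.** A reader might infer that pre-existing antibody will be counted as occurring on OMS721. The text says only that presence is summarised. It leaves the two kinds of positive undistinguished without declaring them all drug-induced.
- **Understatement is not a given.** A reader might infer that each visit shows only a fraction of true incidence. That is so only when positivity is transient.
- **The table shells are separate.** SAP 20.1 says so, and they may contain a shift or any-time row, or a split by arm. This cannot be excluded, but the SAP text makes no such commitment. For the same reason, pooling of the arms is a possibility under the wording and not a certainty.
- **Weight.** The endpoint is exploratory, the study is descriptive and unpowered, and protocol and SAP agree with each other. All true: this is a weakness in the chosen summary and not a conflict between documents.

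What remains is that the planned table, as described, does not answer the question the endpoint poses.

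**Conclusion.** The point holds, as a minor one. The planned by-time summary cannot separate pre-existing from newly arising antibody, cannot show how many subjects ever become positive, and may mix vehicle with OMS721 subjects in Cohorts 2 and 3.

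The illustrative ranges in the working show what one table leaves undetermined. They predict nothing about OMS721, and they rest on 9 subjects, complete sampling, equal counts at each time and a by-arm display that SAP 17 does not state. If positivity persists once it arises, the by-time table understates nothing.

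**What to change.** Keep the by-time summary, present it by disease, cohort and treatment, and add to SAP 17:

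> The number and percentage of subjects ADA-negative at baseline (last sample before first dose, SAP 8.2.1) who are ADA-positive at any later sample (treatment-emergent ADA) will be given by disease, cohort and treatment through Follow-Up Visit 2, and separately for samples after the start of open-label OMS721 re-treatment, using the RT1 pre-dose sample as reference for subjects first randomised to vehicle. Subjects positive at baseline will be shown separately. NAb will be summarised in the same way where NAb results are available.

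The condition on NAb is needed because the schedules list ADA sampling only, and no section says which samples are tested for NAb.

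Two details should be settled with this wording: where FU3 to FU9 samples from subjects never re-treated are counted, and how rollover subjects from Cohort 2 who had vehicle are referenced once they start open-label OMS721.

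The cost is one derived variable and one extra table for an exploratory endpoint, with no new samples or visits. The definition is best fixed before the two Cohort 3 interim analyses in SAP 18, so that it is not chosen after results are seen.
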